## 7 Study Objectives

### 7.1 Primary Objectives

The primary objective of this study is to evaluate the safety and efficacy of pitolisant compared with placebo in treating excessive daytime sleepiness (EDS) in patients with myotonic dystrophy type 1 (DM1) ages 18 to 65 years.

### 7.2 Secondary Objectives

The secondary objectives of this study are to assess:

- The impact of pitolisant on fatigue in patients with DM1
- The impact of pitolisant on selected domains of cognitive function in patients with DM1
- Investigator and patient impression of overall impact of pitolisant on burden of disease in patients with DM1
- Safety and effectiveness of pitolisant during long-term treatment (during the OLE Phase)

## 8 Study Design

### 8.1 General Design

This is a randomized, Double-Blind, placebo-controlled, parallel-group study in adult patients (ages 18 to 65 years) with DM1, followed by an optional OLE Phase.

The study will consist of a Screening Period (up to 45 days), an 11-week Double-Blind Treatment Phase (including a 3-week Titration Period and an 8-week Stable Dose Period), and an optional OLE Phase. The OLE Phase will continue until Day 459/Month 15/Visit 8 for each patient, unless the patient withdraws from the study early or the Sponsor elects to terminate the study. An overall schema of the study design is provided in [Figure 1](#).

After Screening, approximately 30 patients ages 18 to 65 years who meet all eligibility criteria will be randomized at the Baseline Visit in a 1:1:1 ratio to lower dose pitolisant (17.8 mg), higher dose pitolisant (35.6 mg), or matching placebo. In the Double-Blind Treatment Phase, patients will be titrated to their randomized stable dose of study drug during the 3-week Titration Period ([Table 1](#)). After completion of the 3-week Titration Period, patients will continue to take study drug at their randomized dose once daily in the morning upon waking for an additional 8 weeks of blinded treatment (Stable Dose Period). The duration of the Double-Blind Treatment Phase will be 11 weeks. Adjustments to study drug dosing outside of the protocol-specified titration schedule are not allowed during the 11-week Double-Blind Treatment Phase.

Following the 11-week Double-Blind Treatment Phase, eligible patients will be given the opportunity to participate in an optional OLE Phase. During the OLE Phase, all eligible patients will receive treatment with open-label pitolisant and will be titrated during a 3-week Titration Period to a dose of 35.6 mg (or a maximum dose up to 35.6 mg based on Investigator assessment of tolerability) ([Table 2](#)). Adjustments to pitolisant dose are permitted during the OLE Phase; pitolisant dose can be adjusted (higher or lower) based on Investigator assessment of tolerability; the maximum dose allowed is 35.6 mg once daily.

The COVID-19 (Coronavirus Disease 2019) pandemic has had a major impact on the conduct of clinical trials worldwide, including restrictions on travel, dislocation of clinical trial subjects, and the need of many health care facilities to handle an influx of patients with COVID-19. Recognizing the impact of COVID-19 on clinical trials, the National Institutes of Health (NIH) and the U.S. Food and Drug Administration (FDA) released guidance to provide general considerations to assist sponsors in assuring the safety of trial participants, maintaining compliance with good clinical practice (GCP), and minimizing risks to trial integrity

[figure not shown]

for the duration of the COVID-19 public health emergency. Details of analyses of data collected regarding the impact of COVID-19 on this study are included within the applicable sections.

## 8.2 Study and Patient Completion

- Patients who completed the DBT Phase are patients who completed treatment during the DBT Phase and entered the OLE Phase and or patients who completed treatment during the DBT Phase and did not enter in the OLE Phase.
- Patients who completed the study drug who discontinued study drug during the DBT Phase and continued to meet the eligibility criteria for the study.

**Figure 1: Overall Study Design**

Abbreviations: AE = adverse event; BL = baseline; C-SSRS = Columbia-Suicide Severity Rating Scale; EOT = end-of-treatment; F-up = follow-up; MWT = Maintenance of Wakefulness Test; OLE = Open-Label Extension; PK = pharmacokinetics; TC = telephone contact; V = visit.

- a The Titration Period for the Double-Blind Treatment Phase will be from Days 1 to 21. Patients will receive their first dose of study drug on Day 1; study drug dose will be titrated on Day 8 and again on Day 15 (as appropriate based on randomized dose; Table 1); all patients will be at their final randomized dose by Day 15 of the Titration Period.
- b The 8-week Stable Dose Period for the Double-Blind Treatment Phase will be from Days 22 to 77 ( $\pm 3$  days); patients will take their last dose of blinded treatment on Day 77 ( $\pm 3$  days). Visit 5 (Day 77  $\pm 3$  days) is the EOT Visit for the Double-Blind Treatment Phase. The EOT (Week 11) MWT assessment should not be performed on the same day as the Visit 5 PK as patients will take their dose of study drug at the site after ECGs and the pre-dose PK blood draw are done. The EOT (Week 11) MWT may be conducted up to 3 days in advance of Day 77; patients should take their dose of study drug on the morning of the scheduled Week 11 MWT assessment. Eligible patients who opt to enter the OLE Phase will be dispensed OLE study drug for titration at this visit.
- c The Titration Period for the OLE Phase will be from Days 78 to 98 ( $\pm 3$  days). Eligible patients will receive their first dose of open-label pitolisant on Day 78 and pitolisant dose will be titrated on Day 85 and again on Day 92 to a dose of 35.6 mg (or a maximum dose up to 35.6 mg based on Investigator assessment of tolerability). At the end of the 3-week Titration Period, patients will continue to take pitolisant 35.6 mg (or their maximum dose up to 35.6 mg based on Investigator assessment of tolerability) once daily in the morning upon waking until the end of the study (Long-Term Dosing Period). During the OLE Phase, pitolisant dose can be adjusted (higher or lower) based on Investigator assessment of tolerability. The maximum pitolisant dose allowed in the study is 35.6 mg.
- d In between the 6-monthly on-site study visits, patients will receive a TC from the study site approximately every 180 days (i.e., on Days 189 and 369) to record AEs (including inquiries regarding signs and symptoms of arrhythmia, any other cardiac manifestations [e.g., syncope], and psychiatric events [e.g., suicidality, compulsive behavior, anxiety]) and

concomitant medication use, complete C-SSRS, confirm the current dose of study drug and compliance with dosing, and confirm shipment/receipt of study drug sufficient for 3 months (i.e., 90 days) of once daily administration.

e All AEs regardless of seriousness, severity, or causality will be collected from the time the patient provides written informed consent through 30 days (+3 days) after final dose of study drug (Safety Follow-up TCs, Protocol Section 7.4). At the Safety Follow-up TCs, AEs (including inquiries regarding signs and symptoms of arrhythmia, any other cardiac manifestations [e.g., syncope], and psychiatric events [e.g., suicidality, compulsive behavior, anxiety]) and concomitant medication use will be recorded.

f Patients who consent to the optional MWT must return to the study site on the day before the scheduled Baseline MWT assessment and the day before the scheduled EOT MWT assessment of the Double-Blind Treatment Phase.

**Table 1: Study Drug Dosing in the Double-Blind Treatment Phase**

Treatment Groups	Titration Period (3 Weeks)			Stable Dose Period (8 Weeks)
	Week 1 (Days 1 - 7)	Week 2 (Days 8 - 14)	Week 3 (Days 15 - 21)	Weeks 4 - 11 (Days 22 - 77)
Lower dose pitolisant	4.45 mg	8.9 mg	17.8 mg	17.8 mg
Higher dose pitolisant	8.9 mg	17.8 mg	35.6 mg	35.6 mg
Placebo	Matching tablets	Matching tablets	Matching tablets	Matching tablets

Note: Adjustments to study drug dosing outside of the protocol-specified titration schedule are not permitted during the Double-Blind Treatment Phase.

**Table 2: Pitolisant Dosing in the OLE Phase**

	Titration Period a (3 Weeks)			Long-Term Dosing Period b
	Week 12 (Days 78 - 84)	Week 13 (Days 85 - 91)	Week 14 (Days 92- 98)	Weeks 15 (Day 99) to EOT
Pitolisant dose	8.9 mg	17.8 mg	35.6 mg	35.6 mg

Abbreviations: EOT = End-of-Treatment; OLE = Open-Label Extension.

a Pitolisant dose will be titrated on Day 85 and again on Day 92.

b After completion of the 3-week Titration Period, patients will continue to receive pitolisant 35.6 mg (or their maximum dose up to 35.6 mg based on Investigator assessment of tolerability).

Note: Adjustments to study drug dosing after the protocol-specified titration period are permitted during the OLE Treatment Phase of the study, where the pitolisant dose can be adjusted (higher or lower) based on Investigator assessment of tolerability; the maximum pitolisant dose allowed in the study is 35.6 mg (Protocol Section 3.1.2.2) It is recommended that adjustments made during this time be to one of the three pre-specified doses of 35.6 mg, 17.8 mg, or 8.9 mg. If deemed necessary by the Investigator, alternative doses may be prescribed during the OLE Phase; however, the Investigator must first consult with the Medical Monitor. Dosing may be adjusted in increments of 4.45 mg.

### 8.3 Sample Size Considerations

[REDACTED]

### 8.4 Randomization

After Screening, approximately 30 patients ages 18 to 65 years who meet all eligibility criteria will be randomized at the Baseline Visit in a 1:1:1 ratio via an interactive response technology (IRT) to lower dose pitolisant, higher dose pitolisant, or matching placebo. The randomization will be stratified by concomitant use of wake-promoting agents (Yes/No).

Enrolled patients will be allocated a unique identification number in a sequential order; blocks will be dynamically assigned to each stratification level to balance the randomization within each stratification level. Following randomization, Harmony Biosciences will provide all study drug in a packed and labelled kit, and the IRT will identify the kit number to be dispensed to the patient according to the treatment assigned in the randomization schedule.

## 9 Study Endpoints, Conventions and Derivations

### 9.1 Endpoints

Table 3 and Table 4 list the objectives and the assessments being used for the respective endpoints in the study.

**Table 3: Double-Blind Treatment Phase Objectives and Endpoints**

DOUBLE-BLIND TREATMENT PHASE	
Primary Objective	Primary Endpoint
To evaluate the safety and efficacy of pitolisant compared with placebo in treating EDS in patients with DM1.	The change in Daytime Sleepiness Scale (DSS) score from Baseline to Week 11 (Visit 5) for pitolisant compared with placebo.
Secondary Objectives	Secondary Endpoints
To assess the impact of pitolisant on fatigue in patients with DM1.	The change in Fatigue Severity Scale (FSS) score from Baseline to Week 11 (Visit 5) for pitolisant compared with placebo.
To assess the impact of pitolisant on selected domains of cognitive function in patients with DM1.	The change from Baseline to Week 11 (Visit 5) for pitolisant compared with placebo assessment of Cogstate Computerized Cognitive Battery Tests in: 
 
• Identification (Attention), SART (attention), Detection (Psychomotor Function), and One Back (Working Memory).
 

To assess the impact of pitolisant on EDS in patients with DM1.	The change in Epworth Sleepiness Scale (ESS) score from Baseline to Week 11 (Visit 5) for pitolisant compared with placebo.
To assess investigator and patient impression of overall impact of pitolisant on burden of disease in patients with DM1.	The change in score from Baseline to Week 11 (Visit 5) for pitolisant compared with placebo in: 
 
• Clinical Global Impression of Severity (CGI-S) for EDS
 
• Patient Global Impression of Severity (PGI-S) for EDS
 
• Myotonic Dystrophy Health Index (MDHI)
 

Exploratory Objectives	Exploratory Endpoints
To assess the impact of pitolisant on EDS in patients with DM1.	
 
• The change in MSL based on MWT from Baseline to Week 11 for pitolisant compared with placebo.
 

Safety	Safety Endpoints
To assess the safety and tolerability of pitolisant	
 
• Adverse Events (AEs)
 
• Clinical laboratory test results
 
• Vital signs
 
• 12-lead electrocardiogram (ECG)
 
• Holter monitoring
 
• C-SSRS assessment
 
• Physical examinations
 

Abbreviations: CGI-S = Clinical Global Impression of Severity; C-SSRS = Columbia-Suicide Severity Rating Scale; DM1 = Myotonic dystrophy type 1; DSS = Daytime Sleepiness Scale; ECG = electrocardiogram; EDS = Excessive Daytime Sleepiness; ESS = Epworth Sleepiness Scale; FSS = Fatigue Severity Scale; MDHI = Myotonic Dystrophy Health Index; MSL = Mean Sleep Latency; MWT = Maintenance of Wakefulness Test.; PGI-S = Patient Global Impression of Severity; SART = Sustained Attention to Response Task

**Table 4: Open-Label Extension Phase Objectives and Endpoints**

OPEN LABEL EXTENSION PHASE	
Objectives	Efficacy Endpoints
To assess effectiveness of pitolisant during long-term treatment (during the OLE Phase).	
 
• Changes from Baseline in: 
 
○ DSS
 
○ ESS
 
○ FSS
 
○ Cogstate Detection Test, Cogstate SART, Cogstate Identification Test, and Cogstate One Back Test
 
○ MDHI
 
○ CGI-S of EDS
 
○ PGI-S of EDS
 
 
 

Safety	Safety Endpoints
To assess the safety and tolerability of pitolisant	
 
○ AEs
 
○ Clinical labs
 
○ Vital signs
 
○ 12-lead ECG
 
○ Holter monitoring
 
○ Suicidality
 
○ Physical examinations
 

Abbreviations: AE = Adverse Event; CGI-S = Clinical Global Impression of Severity; DSS = Daytime Sleepiness Scale; ECG = Electrocardiogram; EDS = Excessive Daytime Sleepiness; ESS = Epworth Sleepiness Scale; FSS = Fatigue Severity Scale; MDHI = Myotonic Dystrophy Health Index; OLE = Open-Label Extension; PGI-S = Patient Global Impression of Severity, SART = Sustained Attention to Response Task.

## 9.2 Study Day Windows

For each patient there will be a screening period, a Double-Blind Treatment Phase, and an optional OLE Phase.

The study day for data collected after the first dose of study drug will be calculated as visit/assessment date – first dose date + 1. For data collected prior to first dose, the study day will be calculated as visit/assessment date – first dose date. The first dose date refers to the date the study drug was taken for the first time, i.e., at the beginning of the Double-Blind Treatment Phase.

### 9.2.1 Visit Window

The visit window and pharmacokinetic (PK) draw window appear in [Table 5](#) and [Table 6](#), respectively. Unless otherwise stated the endpoints will be analyzed and reported using the analysis visits.

Analysis visit windows will be derived for the Double-Blind Treatment Phase and used for the analyses. For C-SSRS, no analysis window will be applied; data will be reported using the nominal visit. No summary will be created for C-SSRS data, which will be included in a listing only. Therefore, no analysis windowing will be applied on C-SSRS data.

During the Double-Blind Treatment Phase, if a patient stopped taking treatment in the first week of the study (i.e., stopped treatment within 7 days of the date of first dose) for a reason other than an adverse event and then re-started study treatment more than 14 days after the treatment interruption, the analysis visit window

for post-baseline visits will be derived using the date the patient re-started their study treatment (i.e., the visit window will not be based on date of first dose for that patient).

For the OLE Phase, nominal visit will be used.

**Table 5: Analysis Visit Window and Target Day**

Phase	Protocol Visit	Analysis Visit	Target Day	Analysis Visit Window Lower Limit	Analysis Visit Window Upper Limit
Screening	Visit 1	Baseline	-1	- inf	1
	Visit 2				
Double-Blind	Visit 3	Visit 3 (Day 22)	22	2	35
	Visit 4	Visit 4 (Day 49)	49	36	63
	Visit 5	Visit 5 (Day 77)	77	64	Treatment Phase Completion a
OLE	Visit 6	Visit 6 (Day 99)	99	maximum of (92, Treatment Phase Completion)	129
	Visit 7	Visit 7 (Month 9)	279	130	309
	Visit 8	Visit 8 (Month 15)	459	310	489

Abbreviations: OLE = Open-Label Extension.

aIn the Double-Blind Treatment Phase, if the patient did not enter the OLE Phase, the upper limit of the visit window should be the date of the end of the completion of the treatment phase as collection in the CRF; if the patient entered the OLE Phase, the upper limit of the visit window should be the first dose of study drug intake in the OLE.

**Table 6: PK Draw Timing**

Phase	Visit	Target Day	Timepoints
Double-Blind	Visit 3	Day 22	
 
Pre-dose
 
3 hours (±30 minutes) post-dose
 

	Visit 5	Day 77	
 
Pre-dose
 
3 hours (±30 minutes) post-dose
 

### 9.2.2 Data Selection for Multiple Results

**Double-Blind Treatment Phase:** For post-baseline assessments, if there are multiple non-missing results within the same analysis window (including scheduled and unscheduled results), then the non-missing result that is closest to the target date will be used in the analyses; if more than one result is equally close, the result that is after the target date of the assessment will be used. If necessary, time of the assessment (if collected) will be used to determine the record to be selected.

**OLE Phase:** Assessments performed at nominal visits will be used in the analyses/summaries. Unscheduled assessments will only be used to determine worst, lowest and/or highest results post-baseline where applicable.

Twelve-lead ECGs will be collected in triplicate at each nominal visit as prespecified in the protocol. The mean value of the triplicate (or duplicate) at each nominal visit will be derived. The rules defined above for the post-baseline assessments and for the baseline (section 9.3) will be applied to determine which mean values will be summarized. For the overall interpretation, the worst interpretation across the triplicate (or duplicate) for each given nominal visit will be selected first, and then the rules defined above for the post-baseline assessments and for the baseline (section 9.3) will be applied to determine the results to be summarized.

---

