### 11.6.4 Vital Signs

Vital signs will include blood pressure, heart rate, respiratory rate, , and body temperature. Patients will be resting for at least 5 minutes before taking vital signs.

Vital signs results and corresponding change from study baseline values will be summarized at each visit using descriptive statistics by treatment group.

The reference ranges for the vitals are included in [Table 8](#) and will be used to categorize the assessments by Normal, High, or Low. The lowest and highest post-baseline results will be compared with that at the study baseline, and the "shifts" from study baseline will be summarized using the number and percentage of patients in each shift category by treatment group.

All vital signs measurements will be presented in a data listing; height will be presented within the demographic listing.

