### 11.6.6 12-Lead Electrocardiograms

Triplicate 12-lead ECGs will be obtained after the patient has been resting for at least 5 minutes. For clinically significant ECG findings, a follow-up ECG should be performed within 24 hours and again 7 days later to ensure that the abnormality is not worsening. Follow-up 12-lead ECGs may be performed locally and sent to the Investigator for assessment; the Investigator will submit all ECGs done locally to the central ECG vendor.

A core ECG laboratory will manage all ECG monitoring activities. All ECG results along with the investigator's interpretation, including the average of triplicate measurements at each timepoint, will be presented in data listings.

QT values will be presented with the implementation of corrections (i.e., Fridericia's) as defined in International Council for Harmonisation (ICH) Guidelines E14 by the following categories:

Absolute QT interval corrected for heart rate based on Fridericia's formula (QTcF) interval prolongation:

- QTcF interval <450 ms
- QTcF interval 450-480 ms
- QTcF interval 480-500 ms
- QTcF interval >500 ms

Change from baseline in QTcF interval:

- QTcF interval increases from baseline 30-60 ms
- QTcF interval increases from baseline >60 ms

In addition, potential QT prolongations will be categorized as:

- PR interval >300 msec
- QRS duration >140 msec
- PR interval increase from baseline >50%
- QRS duration increase from baseline >40%

- HR increase >65% from baseline
- HR decrease >40% from baseline

The actual values and change from baseline values at each time point will be summarized for the safety populations. The overall interpretation will also be summarized by timepoint as well as the worst post-baseline.

The average of the triplicates at each timepoint will be used in the summaries as defined in [Section 9.2](#).

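### Double-blind QTcF, PR, QRS and heart-rate categories default to one ECG mean per analysis window, so an outlying ECG can be left out of the outlier table

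*SAP*

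**What the plan says.** SAP 11.6.6 lists absolute QTcF categories, QTcF change categories, and criteria for PR, QRS and heart rate. It attaches no counting basis to these lists. Two sentences nearby come closest:

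- On which ECG values to use: "The average of the triplicates at each timepoint will be used in the summaries as defined in" Section 9.2.
- On the qualitative reading: "The overall interpretation will also be summarized by timepoint as well as the worst post-baseline". This covers the overall interpretation, not the numeric categories.

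Section 9.2 then supplies the rules:

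- 9.2.1 sets the default: "Unless otherwise stated the endpoints will be analyzed and reported using the analysis visits".
- 9.2.2, double-blind, lets scheduled and unscheduled results compete within a window, and "then the non-missing result that is closest to the target date will be used in the analyses". Ties go to the later result.
- 9.2.2, for ECGs: "The mean value of the triplicate (or duplicate) at each nominal visit will be derived". The same selection rules "will be applied to determine which mean values will be summarized".
- 9.2.2, under the OLE Phase only: "Unscheduled assessments will only be used to determine worst, lowest and/or highest results post-baseline where applicable".

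Vital signs are handled differently in 11.6.4: "The lowest and highest post-baseline results will be compared with that at the study baseline".

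Protocol 9.4.3 says only that ECG abnormalities are summarised with counts and percentages, which does not settle the basis.

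**The concern.** An outlier table is meant to show how many patients ever crossed a threshold. A rule that keeps the record nearest a target day suits a by-visit mean. For an outlier count it is the wrong filter, because it ignores the size of the value.

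Safety is part of the primary objective. QTcF above 500 ms and a rise above 60 ms are the protocol's own discontinuation thresholds (4.4.1), and Protocol 1.4 states that pitolisant prolongs the QT interval.

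The protocol also generates extra ECGs. A clinically significant ECG finding calls for follow-up ECGs within 24 hours and again 7 days later (6.3.4.2). A clinically significant Holter finding requires an unscheduled triplicate ECG (7.5). Early termination repeats the Visit 5 assessments (7.2.5). The Visit 3 Holter runs for 24 hours from that visit, so any ECG it prompts comes after the Visit 3 ECG and, up to Day 35, falls in the same window.

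What is at stake is an outlier table that shows no case while the discontinuation table shows a withdrawal for QT prolongation.

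**Working it through.** The plan gives no figure to reproduce. The check applies its selection rule to dated ECGs.

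**Inputs.** SAP Table 5 windows: Visit 3, Days 2 to 35, target 22; Visit 4, Days 36 to 63, target 49; Visit 5, Day 64 to completion of the treatment phase, target 77. Visits 3 to 5 may be held within 3 days of target. The ECG days and QTcF values below are illustrative assumptions.

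**Rule.** Keep the record with the smallest |day − target|; on a tie, keep the later one.

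| Case | ECGs in the window | Distance from target | Kept | Outlier counted? |
|---|---|---|---|---|
| A | Visit 3 Day 22, 440 ms; unscheduled Day 28, 505 ms | 0; 6 | Day 22 | No |
| B | Visit 4 Day 49, 440 ms; unscheduled or early-termination Day 60, 505 ms | 0; 11 | Day 49 | No |
| C | Unscheduled Day 40, 510 ms; early-termination Day 45, 450 ms | 9; 4 | Day 45 | No |
| D | Visit 3 Day 19, 510 ms; repeat Day 20, 445 ms | 3; 2 | Day 20 | No |
| E | Visit 4 Day 46, above threshold; early-termination Day 49, below threshold | 3; 0 | Day 49 | No |
| F | Visit 3 Day 19, below threshold; unscheduled Day 23, above threshold | 3; 1 | Day 23 | Yes |

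In case A, follow-up ECGs on Days 29 and 35 would also lie in the window, at distances 7 and 13, and would also lose to Day 22.

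**General form.** If the scheduled visit falls on day v and the target is T, with v before T, a later ECG in the window loses from day 2T − v + 1. For Visit 3 on Day 19 that is 2 × 22 − 19 + 1 = Day 26. If v is on or after T, every later ECG in that window loses.

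**Change categories.** The kept record supplies the change from baseline as well as the absolute value, so a rise above 60 ms on a record that is not kept is lost in the same way. No baseline value is assumed above, so the cases show the absolute category only.

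**If means exist only at nominal visits.** The ECG sentence in 9.2.2 can be read this way. Unscheduled outliers then never enter, so A, C and F are all missed. The repeat in D no longer competes, and that outlier is counted. E is still dropped, because the early-termination ECG belongs to a protocol visit and falls in the Visit 4 window.

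**Timepoints.** Visits 3 and 5 each have pre-dose and 3-hour post-dose ECGs on the same day, which tie on distance. Section 9.2.2 does not say that both are kept.

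**Size.** 30 ÷ 3 = 10 per arm, so one patient is 1 ÷ 10 = 10 percentage points. In the pooled active group it is 1 ÷ 20 = 5 points.

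**Bins.** The 450-480 and 480-500 ms categories both contain 480 ms.

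**The case against.** The strongest reply is that the plan is not silent. Section 9.2.1 makes the analysis visit the default and 11.6.6 states nothing else for these categories, so they are counted by visit. That stands: a reader might infer that the counting basis is wholly undefined, and the documents do not support that. The point is that the default basis is unsuited to an outlier count.

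The second reply is that nothing disappears. All ECG results are listed, QT prolongation at these thresholds requires discontinuation of study drug (Protocol 4.4.1), clinically significant ECG findings are to be recorded as adverse events (6.3.1), and the SAP tabulates events leading to discontinuation. The overall interpretation has a worst post-baseline summary, and with about 30 patients the listings can be read in full. This also stands. A reader might infer that a QT event could be hidden from the report, and the documents do not support that either.

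Third, Holter monitoring is aimed at arrhythmias. It shows that unscheduled ECGs will occur, not that QTcF outliers will be found on them. The documents give no event rate, so no probability of a missed case can be stated.

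Fourth, the vital-signs rule in 11.6.4 does not say that unscheduled double-blind results are included. It shows that extreme values were considered elsewhere in the SAP, but it is not a ready-made rule to copy.

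None of these replies puts a displaced or excluded outlier back into the count.

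**Conclusion.** The point holds, with limited harm. Followed as written, the double-blind rule can leave out a QTcF above 500 ms or a rise above 60 ms when the ECG is unscheduled or from early termination, or when a scheduled outlier is displaced by an ECG nearer the target day. The same applies to the PR, QRS and heart-rate criteria.

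The word is can: an outlier that is nearest the target, or the only eligible record in its window, is kept. Each missed patient shifts an arm's rate by about 10 percentage points, and the resulting table may disagree with the listings and the discontinuation table.

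This rests on the Table 5 windows, on early-termination ECGs being assigned to a window by their day, and on about 10 patients per arm. It does not rest on any assumed frequency of QT events. It is worth correcting before unblinding, but it does not threaten the visibility of the safety data.

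**What to change.** Add to SAP 11.6.6, with a matching line in 9.2.2:

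> For the Double-Blind Treatment Phase, a patient is counted in each PR, QRS and HR criterion if any post-baseline ECG meets it, with HR increase and HR decrease assessed separately. QTcF absolute and change categories use the maximum post-baseline value and the maximum increase from baseline. All scheduled, unscheduled and early-termination ECGs and all pre-dose and post-dose timepoints are included. For each unscheduled ECG the mean of the available tracings is used, or the single tracing if only one exists. By-visit summaries keep the closest-to-target record within timepoint.

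Heart rate needs the separate treatment because its criteria run in both directions, so a single worst value is undefined. The single-tracing clause is needed because follow-up ECGs may be done locally. Also redefine the QTcF bins so that 480 ms falls in only one of them.

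The cost is SAP wording and one extra table program, with no new data. Counts may look slightly less favourable, and the new table will not match the by-visit table row for row; a footnote should say why.
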